**EMA Measures of Symptoms, Medication Adherence, and Socialization (Secondary Outcome):** EMA ratings are single-item, thrice daily 1-7 scales (1 “not at all” to 7 “extremely”) for severity of depression, voices, and mania, along with medication adherence (binary yes or no response) and socialization (number of social interactions).

**Beck Anxiety Inventory (Secondary Outcome):** The BAI is a 21-item self-report inventory rated on a scale from 0 to 3. This will allow us to determine how the subject has been feeling in the last month in terms of severity of anxiety. Each item is related to subjective, somatic, or panic-related symptoms of anxiety and the responses range from “not at all” to “severely”

**Medication Adherence (Secondary Outcome): Self-report:** The Medication Adherence Rating Scale will be used, which asks about the willingness and ability to take your medications every day. It has been used to measure medication adherence in psychosis

**Social Functioning Scale (Secondary Outcome):** We will assess social function with the Birchwood Social Functioning Scale (SFS), a 79-item self-report of social functioning across 7 domains: 1) social engagement, 2) interpersonal behavior, 3) prosocial activities, 4) recreation, 5) independence/competence, 6) independence/performance, and 7) employment. The SFS is

administered in interview (versus self-report) and best estimate ratings are based on observations

**Specific Levels of Functioning Scale (Secondary Outcome):** The SLOF is a multidimensional behavioral survey administered to the caseworker or caregiver of a patient with schizophrenia. The scale assesses the patient's current functioning and behavior across six different domains. We will be looking at only 4 of them: Interpersonal Relationships, Social Acceptability, Activities of Community Living, and Work Skills. Each of these questions is rated on a 5-point Likert scale. The lower the total score means the better overall functioning of the patient.

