**Intervention Procedures (CBT2go, EMA-Only, and Standard Care Conditions):**

**Device:** As in previous trials, we will use the touch-screen Samsung Fascinate, a 4G Android OS smartphone. These devices will have a data plan (and can receive incoming calls). We will provide this device to participants. Participants will be informed that if they lose or damage the device they will not be held responsible.

**Device Training:** Device training covers how to operate the device, the meaning of all questions and response choices, and procedures for carrying the device and responding to alarms. Participants will also be trained in how to access and use crisis lines. This session will be individually-tailored to the learning needs of each participant, until participants can complete a trial run and feels

comfortable with the device. The Project Therapist or PI will be available to answer questions every day.

**EMA Protocol:** Interactions are triggered by a text message sent via an SMS gateway (with a “shortcode” referenced to our study), which automatically opens the browser wrapper that displays questions and alerts participants with vibration or ringtone. The timing can be adjusted to accommodate each participant’s preferences (e.g., sleep and wake schedules) and alarms can be silenced for 30-minute intervals (e.g., during driving). All data entries will be time stamped and responses recorded in real time. Data are accessible at all times only to study staff on a password protected server. If participants stop responding before the end of the questions, the data are still recorded; participants cannot “backfill” surveys as they expire in 15 minutes of the terminal alarm. Labeled on the back of the device is the investigator contact information and crisis line information. Participants will be instructed to answer the surveys and then return with the device at Week 12.

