**EMA Questions:** Participants will respond to surveys three times per day for 12 weeks. The frequency (3 times per day, morning, mid-day, evening) and timing (random initiation at approximately 2 hour intervals) of EMA surveys are based on preliminary data described above. In each of morning, mid-day, and evening surveys, participants will be prompted to answer multiple-choice questions (i.e., they do NOT type in answers) asking: What are you doing? (e.g., working, non-physical leisure), Who are you with? (e.g., alone, with family), Where are you? (e.g., at home, at work), and 7-point Likert scales are used to rate mood and symptoms (e.g., Are you sad? “Not at all” to “Extremely” or Have you been bothered by voices? “No voices” to “Extremely”). They also report whether or not they have taken prescribed medications and the number of social interactions since the last signal. The format of these questions is identical between EMA-only and CBT2go.

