**Power Analysis:** The lack of prior RCTs of mobile interventions in BD or SZ makes it challenging to determine the effect size with which to power the study. The underlying assumption of our RCT is that effect sizes will be comparable to that seen in in-person CBT; Accordingly, we conservatively powered the study based results of recent meta-analyses of CBT in SZ and BD in a total of 46 RCTs, which revealed a median effect size of 0.4 (small to moderate) in favor of CBT with active comparators. Sample size estimates were based on the Hedeker, et al. method for various covariance structures for mixed effects models. For the proposed study, we assumed an autoregressive covariance structure, with conservative correlation between sequential assessments set at 0.5. Using this methodology, assuming an alpha level of 0.05, we have a minimum 80% power to detect a medium effect size with 20% attrition at 12 weeks (based on pilot data) when there are 85 subjects per each condition for a total of 255 subjects.

**Hypothesis 2 (Secondary Outcomes):** Compared to EMA-only and Standard Care, the CBT2go intervention will be associated with greater improvement in EMA and standard lab-based measures of medication adherence, social functioning, and hospitalization and emergency service utilization. **Dependent Variables:** EMA-outcomes; Medication adherence Composite; SFS Score; PSR Toolkit Composite and Hospitalizations/ER visits. **Independent Variables:** Condition and Time (0,6,12,24 Weeks).

**Statistical Analysis:** As above, this hypothesis will be tested using GAMMs. Condition will be entered into the model as a fixed-effect predictor along with time on study and their interaction, and we will test for all pairwise differences (e.g., CBT2go vs. Standard Care) with Westfall-Young adjusted p values. EMA outcomes (which include up to 252 observations per person) will be assessed with Hierarchical GLM analyses with a multinomial sampling model with a logit link functioning, with time (days in study) as a predictor and Condition (CBT2go vs. EMA-only) as a predictor of intercept and growth parameters of the model.

**Power Analysis:** Our secondary outcomes have the same assumptions as those in Hypothesis 1 and thus are independently powered to detect a medium effect size for each measure. The power to detect differences by condition with EMA analyses should be equal or greater by virtue of number of observations.

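### The EMA socialization count covers a window that differs by time of day and between people, but the SAP's EMA model has no term for survey slot

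*Protocol*

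**What the plan says.** Protocol section 9 (EMA Measures of Symptoms, Medication Adherence, and Socialization) makes "socialization (number of social interactions" a secondary EMA outcome. Under EMA Questions, "Participants will respond to surveys three times per day for 12 weeks", in the morning, at mid-day and in the evening, with "timing (random initiation at approximately 2 hour intervals". The item asks for "the number of social interactions since the last signal", so its window has no fixed length. Under EMA Protocol, "The timing can be adjusted to accommodate each" participant's sleep and wake schedule. Unanswered surveys cannot be completed later, "as they expire in 15 minutes of the terminal alarm". The same paragraph states: "All data entries will be time stamped".

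The SAP (Hypothesis 2, Statistical Analysis) assigns the EMA outcomes to a hierarchical generalised linear model with a multinomial logit, "with time (days in study) as a predictor and Condition (CBT2go vs. EMA-only) as a predictor of intercept and growth parameters". Neither document gives a time-of-day term, an elapsed-time term, a daily aggregation rule, or a rule for the count that follows a missed survey.

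**The concern.** A count taken over one window is not the same quantity as a count taken over another. The first survey of the day covers the previous evening, the night and the early morning; the later ones cover only the gap between daytime signals. Because timing is set per person, windows also differ between participants. The model pools all these counts.

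The EMA result for socialization is the effect of Condition on intercept and growth. If the mix of answered morning, mid-day and evening surveys drifts over 12 weeks, and drifts differently in CBT2go and EMA-only, the average window behind the answered counts differs by arm. Part of that difference would then be read as a difference in socialization.

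**Working it through.** **The plan's own figure.** 3 surveys x 7 days x 12 weeks = 252, which matches the SAP's maximum number of EMA observations per person.

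**Inputs.** The item wording, the three slots and the 2-hour spacing come from the Protocol. The documents give no clock times, waking hours or slot-specific response rates. Assumed here: 16 waking hours a day, a constant true interaction rate, and three signal schedules.

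| Assumed schedule | Clock-hour windows (morning, mid-day, evening) | Waking-hour windows |
|---|---|---|
| A: 10:00, 12:00, 14:00 (2 hours apart) | 20, 2, 2 | 12, 2, 2 |
| B: 9:00, 14:00, 19:00 (spread) | 14, 5, 5 | 6, 5, 5 |
| C: spread, shorter morning window | not specified | 4, 6, 6 |

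**Window from the last signal sent.** With response probability p_k and waking window w_k in slot k, the mean waking hours behind an answered survey are sum(p_k w_k) / sum(p_k). If all p_k are equal they cancel, and the mean is 16/3 = 5.333 hours at any response level. A uniform fall in response therefore gives a ratio of 1.00.

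Slot-specific falls, compared with 90% response in every slot:

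| Schedule | Change | Mean waking hours | Ratio to 5.333 |
|---|---|---|---|
| A | morning to 60% | (7.2 + 1.8 + 1.8)/2.4 = 4.50 | 0.84 |
| A | morning to 45% | (5.4 + 1.8 + 1.8)/2.25 = 4.00 | 0.75 |
| A | evening to 45% | (10.8 + 1.8 + 0.9)/2.25 = 6.00 | 1.125 |
| B | morning to 60% | (3.6 + 4.5 + 4.5)/2.4 = 5.25 | 0.98 |
| B | morning to 45% | (2.7 + 4.5 + 4.5)/2.25 = 5.20 | 0.975 |
| B | evening to 45% | (5.4 + 4.5 + 2.25)/2.25 = 5.40 | 1.01 |
| C | morning 30% lower (relative) | (0.7 x 4 + 6 + 6)/2.7 = 5.48 | 1.03 |

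With a constant rate, these are the false ratios of mean counts. Each is also the false arm ratio if one arm has the changed pattern and the other does not. If both arms change alike, the mix of slots is the same in each: the time trend moves, but the Condition contrast does not.

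**Window from the last answered survey.** The mean is 16 / sum(p_k). For 75% against 85% response the ratio is 0.85/0.75 = 1.13; for a fall from 90% to 60% it is 0.90/0.60 = 1.50.

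**Effect of a slot term.** Within a slot, under the last-signal-sent reading and with timing alike in both arms, the expected count is rate x w_k in both arms whatever the response. With no true effect, the arm ratio given slot is 1.00.

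**The case against.** A reader might infer that any fall in compliance inflates the counts, by 13% to 50%, and so favours the arm that answers fewer surveys. The documents do not support this. It needs participants to count back to their last answered survey, whereas the item refers to the last signal, most naturally the prompt that was sent. Device training covers what every question means, but neither document says which reference point is taught. On the literal reading a uniform fall has no effect. The sign of a slot-specific effect depends on the schedule: lower morning response lowers the mean under A and B and raises it under C.

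A reader might also infer that compliance differs by arm because only CBT2go answers branch to intervention content. That is conjecture. The question format is identical in the two device arms, both have a one-hour in-person session and scheduled telephone contact, and Hypothesis 3 concerns cognition and diagnosis as sources of variation in compliance, not arm.

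The obvious remedy, a log-hours offset, also meets a fair objection. An offset belongs to a count model, whereas the SAP names a multinomial logit and the items are multiple choice. Clock hours would also count about 8 hours of sleep as exposure: the morning window under A is 20 clock hours but 12 waking hours.

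These objections limit the size and certainty of the bias. They leave standing that windows differ by slot and person and that the model has no term for this.

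**Conclusion.** The point holds as a minor gap in the specification of one secondary EMA outcome; the BPRS primary outcome is untouched. On the literal reading of the item, bias in the Condition effects needs response to change unevenly by time of day and differently by arm. Both are possible; neither is shown. Given both, the false shift in the mean count is about -2.5% to +3% with signals spread over the day and about -25% to +13% with signals about 2 hours apart. These figures rest on assumed schedules, 16 waking hours, response of 45% to 90% per slot (30% lower in the morning for schedule C) and a constant true rate. They describe mean counts; the shift on the SAP's logit scale depends on response categories that the documents do not give. The 13% to 50% distortions should not be quoted as the expected size, because they need a reference point that the text does not state.

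**What to change.** In the SAP's EMA analysis for Hypothesis 2:

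- Add survey slot (morning, mid-day, evening) as a fixed effect in the socialization model.
- As a sensitivity analysis, add elapsed time since the previous signal and an indicator that the previous survey was missed, both as covariates. Do not use a clock-hour log offset.
- Report survey compliance by arm and slot, so that readers can see whether the condition for bias is met.

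The cost is a few model terms and one table. Slot and missed surveys follow from the existing time stamps. The Protocol says that entries are stamped but not that send times of unanswered prompts are kept; if they are not, the scheduled time can stand in. No new data are needed. The SAP's cover letter says that the trial has completed, so a change to device training is too late, and the added terms should be recorded as a dated addition.

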**We propose to add several measures to the protocol as detailed below.**

**Summary of Measures (Total estimated time= 4 hours baseline; 2.5 hours follow up):**

**Table 1. Summary of Measures in Original and Supplement**

Measure	Specific Aim	Construct Assessed	Time (Min.)
PARENT STUDY			
MINI	Inc/Aim (Moderator)	3 Diagnosis	25
Demographics, Meds	Descriptive	Sample Characterization	15
BPRS	Aim 1 (Primary)	Global Psychopathology	15
EMA Outcomes	Aim 2 (Secondary)	Mood/psychotic symptom severity, medication adherence, socialization	Various

Tablet Routine Quest.	Aim 2 (Secondary)	Self-reported medication adherence	2
Pharm. Record Adherence	Aim 2 (Secondary)	Objective medication adherence	--
Social Functioning Scale	Aim 2 (Secondary)	Social functioning	30
PSR Toolkit	Aim 2 (Secondary)	Objective real-world function	--
MCCB (Baseline Only)	Aim 3 (Moderator)	Cognitive Impairment	60
Beck Cog. Insight Scale	Aim 3 (Mediator)	Self-reflectiveness and evaluation	10
Dysfunc. Attitudes Scale	Aim 3 (Mediator)	Maladaptive attitudes	10
Columbia Suic. Severity	Safety	Suicidal ideation and behavior	10
NEW MEASURES FROM SUPPLEMENT			
Scale for Suicidal Ideation	Supplement 1,2	Aim Suicidal ideation	10 (B,6,12,24)
Reasons for Living Inventory	Exploratory	Deterrents to Suicide	10 (B, 12)
Iowa Gambling Task	Supplement Aim 1	Impulsive decision making	15 (B)
UPPS Impulsivity Scale	Supplement Aim 1	Impulsive traits	15 (B)
ER40	Supplement Aim 1	Social emotion recognition	5 (B,12)
Interpersonal Needs Ques.	Supplement Aim 1	Social beliefs related to suicide risk	5 (B,12)

**Diagnosis and Background Characteristics:** Diagnosis will be obtained by administering the Mini-International Neuropsychiatric Inventory (MINI), rather than the more lengthy SCID.

**Global Psychopathology (Primary Outcome):** The primary outcome will be the Brief Psychiatric Rating Scale – 24 item expanded version 4.0 (BPRS-24). The BPRS-24 is a clinician rated measure that includes 24 items that cover depression, anxiety, mania, suicidality, delusions/hallucinations, and unusual behavior.

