**PSR Toolkit (Secondary Outcome):** The PSR Toolkit is used to collect objective information on employment, residential situation, and hospitalizations/ER visits. The measure requires no subject testing burden, because research staff complete the PSR Toolkit (with participant release of information) by obtaining medical records, employment status records, visiting residential settings to determine level of services (With release of information for each of these obtained).

**Columbia-Suicide Severity Rating Scale (Secondary Outcome):** The C-SSRS is a semi-structured interview used to measure both behavior and ideation of suicidality. It is evidence-based, and well-supported.

**Cognitive ability (Moderator, Baseline only):** Cognitive ability will be measured with the MATRICES Consensus Cognitive Battery (MCCB) developed through systematic selection and psychometric evaluation of the tests involved.

**5 Choice-Continuous Performance Task (5C-CPT):** The 5C-CPT is a computer task of sustained attention and response inhibition that was developed based on a rodent paradigm.

**Suicide Related Phenotypes:** As noted above, we already administer the Columbia Suicide Severity Rating Scale (CSSRS) Lifetime (baseline) and Interval assessments (follow-ups). The CSSRS is part of the PhenX Suicide Specialty Collection. The CSSRS provides indices related to active ideation and behavior, but we lack more subtle measures of ideation or protective factors. The SSI will be the primary dependent variable for Supplement Aims 1 and 2.

- **Scale for Suicidal Ideation (Baseline, 6, 12, 24):** The Scale for Suicide Ideation (SSI) is a 21-item, interviewer-administered scale assessing intensity attitudes, behaviors, and plans to commit suicide on the day of the interview. This scale will provide additional continuous information about the intensity of current ideation beyond that already collected in the CSSRS. We will omit the final 2 questions that concern historical attempts, because that information is already gathered by the CSSRS. The SSI is a recommended measure from the Suicide Specialty Collection of the PhenX toolkit.

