**Quality Assurance:** The PI will train and supervise raters by reviewing videotapes of interviews. Consistency between raters will be established prior to data collection using gold standard videos, with a standard inter-rater agreement of 0.80. Checks of inter-rater reliability will be conducted semi-annually thereafter. To preserve the blinding of the study and minimize rater bias, raters will not be involved in the treatment. Participants will also be instructed not to disclose their treatment assignment during assessments. If such disclosure is made, the rater will stop the assessment and another rater will continue the assessment.

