A subset of 30 Bipolar participants in the EMA-only condition who indicate interest on their consent form (see below) will be approached about obtaining a total of 3 blood draws and cognitive assessments over the first two weeks of the study by participating in two additional encounters. During their in-person session, these participants will undergo the consenting process for these additional procedures, and if they agree to participate, they will immediately be administered the 5 Choice Continuous Performance test of attention and have 5 ml of blood drawn by a trained phlebotomist on staff. Blood pressure will also be measured. This will add one hour to the in-person session for eligible and willing participants. On day 7 (plus or minus 2 days if necessary for scheduling) **Home Visit 1** will occur in the participant's home. A phlebotomist will draw a blood sample of 5 ml, obtain a blood pressure measurement, and administer the 5 choice continuous performance task and digit symbol coding subtest from the MCCB battery. To assess for suicidal ideation, participants will be asked to complete the Columbia Suicide Severity Rating scale. Home Visit 1 is estimated to last 1 hour. On day 14 (plus or minus 2 days if necessary for scheduling) **Home Visit 2** will occur with the same assessments as Home Visit 1. Home Visit 2 is estimated to last 1 hour.

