## 15. RISK MANAGEMENT PROCEDURES AND ADEQUACY OF RESOURCES

**Assessment:** During in-person interviews, trained raters will closely monitor for signs of stress, fatigue, and distress. Rest breaks will be provided as needed during all assessments to reduce fatigue and boredom. Also, subjects may refuse to answer any specific questions or to complete any given tests. We provide snacks, water and recommend breaks to participants if they report feeling fatigue. We also provide participants the option of splitting the assessments, particularly the baseline assessment which is longer than the other assessments, on different days. They will also be advised that they can withdraw from the study at any point and can still receive the compensation. If a participant discloses that he or she is experiencing suicidal ideation during diagnostic interviewing or on standard clinical measures, the rater will immediately contact the PI to ensure that steps are taken to ensure the participant's safety. The two measures that directly elicit information about current suicidal thoughts are the Columbia Suicide Severity Rating Scale and the Scale for Suicide Ideation. Any report of ideation on these instruments that exceeds "none" will result in an immediate contact to the PI to ensure participant safety. These steps will include a formal risk assessment and may lead to contacting the participant's providers (with signed consent to do so) and arranging emergency care for the participant. Our research center has a Clinical Response Team (of which the PI is the Associate Director) that will provide additional back-up; this team includes board-certified psychiatrists and psychologists who will be available and on site at all times.

**In-Person Session (CBT2go):** The Project Therapist will receive intensive training from supervising psychologists and will be provided supervision on a weekly basis by [name]. Participants will be closely monitored and additional (in session) assistance will be provided to those participants experiencing frustration or distress. Should a participant be observed to be exhibiting an acute symptom exacerbation and/or suicidal or homicidal ideation, the Project Therapist member will notify Drs. [name] or [name] immediately and they will conduct a formal evaluation of the participant with

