additional back-up from the Clinical Response Team. Given that all participants must be currently participating in stable outpatient care, the need for immediate emergency services will be unlikely. Nevertheless, based on our experience conducting clinical research in serious mental illness, we have developed the above plan to intervene appropriately should such a need arise.

**Experimental Conditions (Week 1 through Week 12):** Participants in the CBT2go and EMA-only conditions will be provided a smart-phone device with which to answer questions about their mood, activities and contexts. After baseline interview (and in-person session if in the CBT2go condition), participants will be asked to respond to questionnaires on the device until Week 12. Participants in the Standard Care condition will not be provided a device. We have taken several steps to ensure participant safety during the periods of no in-person contact. All participants will be provided with staff contact information and emergency resources in a printed manual, and they will be instructed that they may call the PI or project manager at any time in case of questions or emergencies. Participants must provide release of information for our staff to contact treating psychiatrists or other appropriate healthcare provider, so any emergent crises will be relayed to that participant's provider. In the CBT2go and EMA-only condition, responses at the severe spectrum of the mood or voices scales are accompanied with a screen that instructs participants to contact both emergency services (911 can be directly accessed via the device) AND project staff, if in crisis. We will monitor these protocols during the course of the study and will make adjustments to inclusion/exclusion criteria in case of adverse events.

**Data and Safety Monitoring Board:** The study will be reviewed annually through the UCSD DSMB. The board consists of non-UCSD faculty in psychiatry, community members, and bioethicists.

**Blood Draw:** Blood samples will be drawn only by research staff trained and certified in phlebotomy. Staff will take care to assure the participant is comfortable and participants will be provided with the necessary medical equipment (e.g. band-aids) to care for any irritation at the site of the blood draw.

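### Does the blood-draw sub-study, run only in EMA-only bipolar participants, unblind the BPRS raters or distort the arm comparison?

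*Protocol*

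**What the plan says.** **Sub-study.** Protocol section 9 (EMA-only Single In-Person Session) restricts it to "A subset of 30 Bipolar participants in the EMA-only condition who indicate interest on their consent form"; section 11 repeats the restriction. The first draw takes place at the EMA-only in-person session. Two home visits of about an hour each follow, on days 7 and 14 (each plus or minus 2 days). The home visits are given to a phlebotomist, and section 24 also names a staff phlebotomist. Section 15 says: "Blood samples will be drawn only by research staff trained and certified in phlebotomy". On the C-SSRS at the home visits, section 9 says: "To assess for suicidal ideation, participants will be asked to complete the Columbia Suicide Severity Rating scale". It does not say who administers it.

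**Blinding.** Under Quality Assurance in section 9, "raters will not be involved in the treatment". It adds: "Participants will also be instructed not to disclose their treatment assignment during assessments". If a participant does disclose, the rater stops and another takes over. The primary outcome depends on these rules: "The BPRS-24 is a clinician rated measure that includes 24 items".

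**C-SSRS.** Section 9 says "we already administer the Columbia Suicide Severity Rating Scale (CSSRS) Lifetime (baseline) and Interval assessments (follow-ups". Its own paragraph in section 9 labels it a secondary outcome, and Table 1 lists it under safety. The SAP does not list it as a dependent variable. Under section 15, any reported ideation above none "will result in an immediate contact to the PI to ensure participant safety", and emergency care may be arranged.

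**SAP.** Hypotheses 1 and 2 are analysed at weeks 0, 6, 12 and 24. Hospitalizations and ER visits are a Hypothesis 2 outcome. The SAP does not mention the sub-study.

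**The concern.** CBT2go against EMA-only is the contrast that isolates the CBT content. Both arms carry a phone, so a phone seen or mentioned at an assessment does not tell the two apart. A home visit for blood sampling does, because within this trial it happens only in EMA-only. Read literally, the blinding rules cover treatment and treatment assignment, and a remark about a blood draw is neither. A rater who expected CBT2go to do better could then score EMA-only participants as worse, which would favour CBT2go on the primary outcome.

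Two further effects seemed possible. If a follow-up C-SSRS covers the time since the previous rating, week 6 spans fewer days in sub-study participants than in everyone else. And each extra rating is another chance for a safety response that ends in an ER visit, which the SAP does analyse.

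**Working it through.** The concern disputes no figure in the plan, so there is nothing to reproduce. The check is of reach, of whether the documents show a route to the rater, and of what enters an analysis.

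**1. Reach.** The inputs are 30 sub-study participants (protocol section 9), 85 per arm (SAP, Hypothesis 1 power analysis) and three follow-up visits.
- Share of the arm: 30/85 = 35%.
- Follow-up BPRS ratings: 30 × 3 = 90 of the arm's 85 × 3 = 255.
- CBT2go and Standard Care: none.

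**2. Is there a route to the rater?**
- The visits belong to a phlebotomist. Raters are trained separately, against reference videos to an agreement standard of 0.80. No passage puts a rater at a sub-study visit.
- The first draw is part of the EMA-only treatment session, so keeping raters out of treatment plausibly keeps them out of it too.
- Section 12 puts the question about interest in the extra procedures to all participants, so stated interest reveals nothing.
- Section 12 of the protocol concerns consent; section 9 allows concurrent enrolment in a separate study of inflammation in bipolar disorder, without limiting this to one arm. A remark about blood sampling might therefore not point to EMA-only, although the documents do not say that the other study draws blood.

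This is a possible leak, not a built-in disclosure.

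**3. Size if it leaked.** Shift in the EMA-only mean = (sub-study share) × (fraction of those ratings unblinded) × (shift per unblinded rating). The last two terms are assumptions.

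| Sub-study size | Fraction unblinded | Shift per rating (SD) | Shift in arm mean (SD) | Share of the 0.4 planning effect |
|---|---|---|---|---|
| any | 0 | any | 0 | 0% |
| 10 | 20% | 0.1 | 0.002 | 0.6% |
| 30 | 20% | 0.2 | 0.014 | 3.5% |
| 10 | 100% | 0.1 | 0.012 | 3% |
| 30 | 100% | 0.1 | 0.035 | 9% |
| 30 | 100% | 0.2 | 0.071 | 18% |
| 30 | 100% | 0.5 | 0.176 | 44% |

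For scale, 20% attrition leaves 85 × 0.8 = 68 per arm. A simple endpoint comparison then has standard error √(2/68) = 0.17 SD, so 0.071 SD is about 0.4 of a standard error. The last row would matter, but it needs every rating unblinded and a large shift in each.

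**4. C-SSRS.** A sub-study participant has 5 post-baseline ratings (days 7 and 14; weeks 6, 12 and 24), against 3 for others. None enters an analysis in the SAP.

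If the look-back ran from the previous rating, week 6 would cover 42 − 14 = 28 days instead of 42. Assume 30% report ideation over 42 days at a constant rate. Then 28 days gives 1 − (1 − 0.30)^(28/42) = 21.2%. The EMA-only figure would be (0.300 − 0.212) × 30/85 = 3.1 points low.

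That needs the undefined look-back to be read in this way, full uptake, the assumed rate, and a between-arm analysis that the SAP does not contain. If the follow-up interval runs between main-study visits, the difference is zero. The Scale for Suicidal Ideation, the dependent variable for the Supplement Aims, is rated for the day of the interview, so its window is unaffected.

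**5. ER visits.** Full uptake adds 30 × 2 = 60 ratings. Assuming 10% to 40% above none, and emergency care arranged in 2% to 10% of those, the extra events run from 60 × 0.10 × 0.02 = 0.1 to 60 × 0.40 × 0.10 = 2.4. Both rates are assumed; the documents say only that such care may be arranged.

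**The case for a change.** The strongest case for a change runs as follows. The arm can be inferred with certainty from a sub-study visit. The blinding text does not name that visit. The C-SSRS is a semi-structured interview, and the protocol does not say who gives it at home, so a trained rater might be asked to. The protocol calls the C-SSRS a secondary outcome yet leaves its follow-up interval undefined. A sentence or two would close all of this at almost no cost.

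Much of this stands. The restriction to one arm, the two added ratings, the unnamed C-SSRS interviewer and the SAP's silence are all in the documents.

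What does not stand is the step from an unwritten detail to a wrong result. A CBT2go participant who mentions thought-challenging messages gives away the arm just as plainly, and the protocol meets that with the same general rule. A rater who understood the purpose of the rule would treat a home visit for blood sampling in the same way. The C-SSRS follow-up intervals read naturally as running between the main-study visits, and an analyst comparing arms would use the visits that all arms share.

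**Conclusion.** No change to the plan is needed. The documents show a possible route to unblinding in up to 35% of one arm. They do not show that it operates, and its size is unknown: zero if no rater learned of the visits, and 0.04 to 0.07 SD if all ratings of all 30 were unblinded and shifted by an assumed 0.1 to 0.2 SD. The conclusion rests on the separation of phlebotomist and rater, the stop-and-replace rule and the SAP's analysis times, not on those assumed sizes. It would weaken if trial records showed that home-visit staff also rated the BPRS, which no passage suggests. The C-SSRS and ER figures are products of assumed rates and carry no weight of their own.

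There is also little to gain. The SAP's cover letter says the trial has completed, so new blinding instructions could not affect the data. Setting sub-study participants' BPRS ratings to missing would remove data from one arm, one diagnosis and a self-selected group, and could add bias of its own. The gap is one of detail. Treating mention of the sub-study as disclosure, and comparing C-SSRS ratings only at common visits, is how the existing rules would sensibly be applied.
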